5.4 Preparation and Administration of Study Drug

BTX-A is supplied as a freeze-dried crystalline complex, in single-use vials of 100 Units. The preparation also contains 0.5 mg of human albumin and 0.9 mg of sodium chloride. For the purpose of this study, vials of 100 units will be used for the unilateral and bilateral breast reconstructions, respectively. Prior to injection, the Research Pharmacy at Mayo Clinic will reconstitute each vacuum-dried vial of BTX-A with non-preserved 0.9% Sodium Chloride Injection USP for a final BTX-A concentration of 2 units/0.1 mL. Thus, the total volume of solution (BTX-A or placebo) injected in each pectoralis major muscle will be 5 mL (or 100 units of BTX-A). The study drug and placebo will be sent to the operating room in single-use vials and administered by the plastic surgeon.

Prior to injection, each vacuum-dried vial of BOTOX® will be reconstituted with sterile, non-preserved 0.9% Sodium Chloride Injection USP. The proper amount (5 mL) of diluent will be drawn in an appropriate size syringe, and the diluent will then be slowly injected into the vial. The vial will be discarded if a vacuum does not pull the diluent into the vial. The BOTOX® will then be mixed gently with the saline by rotating the vial. The date and time of reconstitution will be recorded on the space on the label. BOTOX® will be administered within 24 hours after reconstitution. During this time period, reconstituted BOTOX® will be stored in a refrigerator (2° to 8°C).

Injection protocol:

The surgical team will receive one single-use vial (for unilateral cases) or two single-use vials (for bilateral cases) containing the study drug from the research pharmacy. The contents of each vial will be transferred into one or two appropriate size sterile syringes using an 18-gauge needle. A 22-gauge spinal needle will be used to perform the injections.

The injection of the study drug will occur once the creation of the subpectoral pocket is completed, and AFTER ALL IRRIGATIONS OF THE SURGICAL FIELD to avoid aspiration of the study drug with the suction. The plastic surgeon will inject 1 mL of solution (BTX-A or placebo) at five equidistant points in the inferior third of the pectoralis major muscle.

5.5 Subject Compliance Monitoring

To assure adherence to the one-time intraoperative study drug intervention, the study coordinator will review documentation of intraoperative medications. Monitoring adherence of timely questionnaire completion at each tissue expansion visit will also occur. For patients who will undergo tissue expansions at Mayo Clinic, the study coordinator will ensure that the questionnaires have been fully completed by the study participants before they leave the premises.

In some instances, study participants will not return to Mayo Clinic for each tissue expansion visit. The study coordinator will prepare a packet for these women that will include 7 questionnaires and 7 prepaid return envelopes by post. The study participants are to fill out and return one copy of the questionnaire at each tissue expansion visit performed at an outside institution. To maximize the response rate, we will use the methodology recommended by Dillman⁷³. If the questionnaire is not returned within one week after the planned tissue expansion visit, the study coordinator will contact the patient, and complete the questionnaire by phone. A telephone script will be used for this purpose. If the patient cannot be reached by phone, a reminder will be sent along with one additional copy of the questionnaire.

5.6 Prior and Concomitant Therapy

As part of the standard of care at Mayo Clinic, patients are offered optional regional anesthesia in the form of a thoracic paravertebral block (PVB) on the morning of surgery, in addition to the routine procedures. The PVB technique^{74, 75} used includes multilevel injections of 1% to 0.5% ropivacaine with 1:400,000 epinephrine into the ipsilateral paravertebral space at six levels from T1 through T6. This technique can improve postoperative pain control for 4 to 8 hours after performance of the PVB. The data on PVB will be collected as it can act as a potential confounding variable.

Depending on individual surgeon practice and preference, some patients may receive other forms of short-term intraoperative local analgesia such as Exparel, an injectable suspension of bupivacaine liposome which can provide pain relief for up to 72 hours. Data on Exparel will also be collected as it can act as a potential confounding variable.

Additional oral analgesic intake by study participants will not be monitored as this data collection is often incomplete and of poor quality, making it difficult or impossible to draw any reliable conclusions. Thus, oral analgesic intake will not be restricted during the course of this study.

5.7 Packaging

Allergan, Inc. will provide 180 vials of BOTOX® (100 unit vials) for the purpose of this study. As part of this agreement, Allergan, Inc. will ship 50% of the study drug upon:

1. Full execution of the Letter of Agreement by authorized representatives of the parties;
2. Confirmation that the study has been registered on ClinicalTrials.gov;
3. Approval of the study protocol by the appropriate IRB (if required);
4. The FDA has not placed the IND on clinical hold (if applicable);
5. At least 30 days have elapsed since FDA's official receipt date of the filed IND (if applicable)

The remaining 50% of the study drug will be shipped by Allergan upon enrolling 50% of the target enrollment. If for storage and shelf-life reasons less materials should be sent than indicated above, shipments can be divided up to the maximum-contributed materials amount.

BOTOX® will be supplied in a single-use vial in the following size:

- 100 Units NDC 0023-1145-01

Vials of BOTOX® have a holographic film on the vial label that contains the name "Allergan" within horizontal lines of rainbow color. In order to see the hologram, the vial should be rotated back and forth between the fingers under a desk lamp or fluorescent light source. (Note: the holographic film on the label is absent in the date/lot area.) If the lines of rainbow color or the name "Allergan" cannot be seen, the product will not be used and Allergan will be contacted immediately for additional information at [name] from 7:00 AM to 3:00 PM Pacific Time.

5.8 Blinding of Study Drug

Treatment blinding and randomization will be done by each site specific Mayo Clinic Research Pharmacy. The research pharmacy will prepare BOTOX® or placebo (0.9% Sodium Chloride Injection USP) according to the randomization. The BOTOX® and placebo will look identical in the syringe after preparation. The labels used for both products are also identical. The final prepared product that will be provided to the surgeon will be labeled "For Investigational Use Only".

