3.1 General Design

EXPERIMENTAL DESIGN FOR SPECIFIC AIM#1: To determine the effect of BTX-A on pain and physical well-being during the expansion period in women undergoing subpectoral placement of tissue expanders for two-stage implant-based breast reconstruction.

Research Design: The study design chosen to test our working hypothesis and answer our specific aim is a multi-center, double-blinded, placebo-controlled, prospective, randomized trial. Women at least 18 years of age, who will undergo immediate unilateral or bilateral tissue expander reconstruction, will be recruited to participate in the study.

Consecutively enrolled eligible women will be randomized into one of two different treatment groups, described in section 5.3. Expected duration of subject participation is 4 months.

Study Timeline and Feasibility:

PROPOSED PROJECT TIMETABLE				
AIMS/TASKS	YEAR 01	YEAR 02	YEAR 03	YEAR 04
Specific Aim #1:				→
• Enrollment		→		
• Follow-up		→		
Data Analysis			→	→

For this study, we plan to accrue up to 134 patients in order to obtain a sample size of 128 subjects (64 women per group). Based on annual operative volumes at Mayo Clinic Rochester, and considering that not all plastic surgeons performing tissue expander breast reconstruction will be contributing to

the study, we estimate that approximately 150 women will be eligible for recruitment over a 36-month period, ensuring the feasibility of adequate sample size recruitment (see table below).

Annual numbers of breast reconstructions with tissue expanders at Mayo Clinic Rochester (2008-2010)

Procedure Year	Unilateral tissue expander breast reconstruction	Bilateral tissue expander breast reconstruction	TOTAL
2008	98	123	221
2009	74	111	185
2010 (10 months)	70	107	177

We anticipate that these numbers will remain approximately constant. It is estimated that subjects will be recruited over a 40-month period, and each participant will be followed for 4 months with data collected longitudinally over this period. The last women enrolled in year 1 will be followed for 4months into year 2. Data analysis will commence in year 2.

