5.3 Method for Assigning Subjects to Treatment Groups

Methods: Consecutive women who elect to pursue breast reconstruction with tissue expanders will be approached to participate in this study. All consenting subjects will be randomized to receive either a single dose of 100 units of BTX-A per breast, or a placebo. Study participants will not be blinded regarding the use of ADM at the time of surgery.

Treatment group assignment:

STUDY ARMS	ASSIGNED TREATMENT
1	BTX-A +/- ADM
2	Placebo +/- ADM

Randomization and Masking: Treatment blinding and randomization will be carried out in the hospital's Research Pharmacy Service using a program to generate random numbers. The injected solutions of BTX-A and placebo (0.9% Sodium Chloride Injection USP) will be prepared by the pharmacy service to ensure masking. At the time of injection in the pectoralis major muscle, neither the treating surgeon nor the study participants will be aware of group allocation with regards to the use of BTX-A or placebo. All research team members involved in the assessments and analysis of the data will be blinded. Thus, only the pharmacy personnel preparing the syringes will be aware of group assignment (Group A or B).

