5.9.4 Return or Destruction of Study Drug

At the completion of the study, there will be a final reconciliation of drug shipped, drug consumed, and drug remaining. This reconciliation will be logged on the drug reconciliation form, signed and dated. Any discrepancies noted will be documented and investigated, prior to return or destruction of unused study drug. Drug destroyed on site will be documented in the study files.

6 Study Procedures

TABLE OF VISITS:

	Research activity	Subject activity
Preoperative evaluation/Surgical listing appointment	Study Coordinator (SC) reviews the study with eligible patients and obtains informed consent	Complete the BREAST-Q and Numeric Pain Intensity Scale
Surgery	Randomization by site specific research pharmacy and intra-operative injection of study drug by plastic surgeon	•
First post-operative visit: • Week 1- 2	SC facilitates completion of questionnaire and assesses for adverse events	Complete the BREAST-Q and Numeric Pain Intensity Scale
Subsequent Plastic Surgery Appointments/Expansion Visits • Beginning at week 2-3 and intervals thereafter as determined by the plastic surgeon	SC facilitates completion of questionnaire and assesses for adverse events	Complete the BREAST-Q and Numeric Pain Intensity Scale
• End of Study • The last plastic surgery appointment prior to removal of the TE, or the date of TE removal (whichever occurs last within the 4 month postoperative period)		

Tissue expander placement: The surgical procedure for submuscular placement of the tissue expander will be performed in the usual manner by each participating plastic surgeon.

BTX-A Injection Protocol: see Section 5.4

Outcome Assessment: The outcome measures selected to test our working hypothesis and answer our specific aim #1 are a numeric pain intensity scale (NPIS)⁷¹, and the Physical Well-Being scale of the BREAST-Q®: Reconstruction Module. These two measures will be administered to study participants at the pre-operative visit, the first postoperative visit (1-2 weeks), and subsequent Plastic Surgery appointments/expansion visits until the end of the study is reached.

7 Statistical Plan

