There are two primary outcomes: pain intensity measured by the NPIS, and physical well-being using the BREAST-Q®. The primary analysis will be performed during the post-operative period and during the expansion phase. Outcome variables will be summarized with frequency counts and percentages or means, standard deviations, medians, and ranges, as appropriate. The mean, median, standard deviation, and range of each variable and its change from baseline, measured on a continuous scale, will be presented by treatment and visit. Frequency tables will be provided for categorical variables by treatment and visit. Any differences among the study groups will be evaluated using two-sample t, Wilcoxon rank sum, Pearson's chi-square, or Fisher's exact tests.

Secondary Hypotheses:

- 1) There will be no difference in the initial percent volume expansion between groups (defined as initial intraoperative fill volume divided by manufacturer recommended total tissue expander volume);
- 2) The rate of tissue expansion will be higher in the BTX-A groups compared to the placebo group, with or without the use of ADM;
- 3) There will be no difference in the rate of reconstructive failure (tissue expander removal for reasons such as infection or uncontrolled pain).

The volume of tissue expansion anticipated and the rate of tissue expansion between the BTX-A groups and the placebo and control groups will be calculated both as an absolute value as well as a percentage. It is hypothesized that the use of BTX-A may increase the rate of tissue expansion, which may lead to fewer postoperative tissue expansion visits. This will allow measurement of effect size between the intervention and the placebo groups. Two-sample t and Wilcoxon rank sum tests will be used for the secondary analyses.

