8.6.2 Independent Data and Safety Monitoring Board

Data Safety and Monitoring Board (DSMB): An independent Data Safety and Monitoring Board will consist of [name], [name], [name], [name], [name], [name] and a Mayo Clinic statistician who is not involved with this project. The Data Safety Monitoring Board will assess safety and efficacy at interim analysis (when 75 patients have been enrolled). The Board will be empowered to recommend continuation, modification, or early closure of the trial. Recommendations of the Data Safety Monitoring Board will be reviewed by the Steering Committee who will make the final decision to terminate accrual early. In addition, patient safety will be protected by open communication and reporting of patient safety concerns by any personnel involved in the study to the principal investigator or Trial Steering Committee members during the course of patient participation in the study. If significant issues arise they will be reported to both institutional IRBs for further consideration.

9 Data Handling and Record Keeping

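### The documents disagree on whether the trial has one site or several; if each site's pharmacy randomises, the planned comparisons should include site

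*Combined protocol and SAP*

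**What the plan says.** On the number of sites and who randomises, the text points both ways.

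- **Several sites.** Section 3.1 says the design "is a multi-center, double-blinded, placebo-controlled, prospective, randomized trial"; the Abstract and the overall aim in Section 2 also say multi-center. Section 5.8 states: "Treatment blinding and randomization will be done by each site specific Mayo Clinic Research Pharmacy". The table of visits in Section 6 repeats it: "Randomization by site specific research pharmacy and intra-operative injection of study drug by plastic surgeon". Sections 5.9.1 and 5.9.2 have supply and storage at site-specific pharmacies. Section 8.6.1 gives the Steering Committee site-specific representatives. Section 8.6.2 has significant issues "reported to both institutional IRBs".
- **One site.** The précis lists the trial as single-site. Section 5.3 has randomisation "carried out in the hospital's Research Pharmacy Service using a program to generate random numbers". The feasibility figures in Section 3.1 come from one hospital. Section 8.6.1 refers to a single institutional IRB.

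No section states blocks, strata, or whether there is one list or one per site. Sections 3.1 and 7.1 plan 64 women per arm, which implies 1:1 allocation overall.

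On the analysis, Section 7.2 says: "Any differences among the study groups will be evaluated using two-sample t, Wilcoxon rank sum", or chi-square or Fisher tests for categorical outcomes. The précis gives the same set, and the secondary analyses use the t and Wilcoxon tests. Covariates are allowed only in sensitivity analyses, where the baseline tables suggest they are needed. Site is not among the variables named, although that list is open-ended.

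**The concern.** If each pharmacy randomises its own women, site is a stratum of the randomisation, and an analysis that pools across sites does not reflect how allocation was done. The usual rule is to analyse by the factors used to randomise. Otherwise the standard error can be wrong for the design, and precision that the design has bought goes unused.

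The protocol gives some reason to think site could matter. Expansion intervals are set by the surgeon and expanders are placed in each surgeon's usual way (Section 6). Long-acting local analgesia depends on surgeon preference (Section 5.6). These bear on pain and on rate of expansion, and they may cluster by site. No section reports an actual difference between sites, so this is a possibility only.

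At stake are the efficiency and calibration of the NPIS and BREAST-Q comparisons. The sample size has little slack: 64 per arm gives 80% power for a 1.0-point difference only at the lowest SD in the Section 7.1 table (61% at SD 2.5).

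**Working it through.** **Inputs from Section 7.1.** Difference 1.0 point (4.0 against 3.0), SD 2.0, alpha 0.05, power 80%, two-sample t-test, 64 complete per arm.

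**Assumptions, not in the documents.** Two sites; 50% or 25% of women at the second; equal allocation at each site; a share f of total outcome variance due to site, f = 5%, 10% or 20%. Total SD is held at 2.0, because Section 7.1 uses its SDs in a pooled t-test.

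**Step 1: the plan's figure.** A two-sided two-sample t-test gives n = 63.77, so 64 per arm, with power 80.1%. The other five rows also reproduce (17, 26, 100, 37, 143). The standard error of the difference is 2.0 × √(2/64) = 0.354.

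**Step 2: what f means in points.** With second-site share p, the gap in mean pain between sites is √(f × 4 / [p(1 − p)]). For f = 5%, 10% and 20% this is 0.89, 1.26 and 1.79 points at p = 50%, and 1.03, 1.46 and 2.07 points at p = 25%. The top of the range is thus a site gap about twice the target treatment effect.

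**Step 3: lists blocked within site.** The arms are balanced by site, so the true variance of the difference is (1 − f) times what the pooled test assumes.

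- True alpha = 2 × [1 − Φ(1.96/√(1 − f))].
- Unadjusted power ≈ Φ((1/0.354 − 1.96)/√(1 − f)).
- Adjusted power: t-test with SD 2.0 × √(1 − f).

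| f | True alpha, unadjusted | Power, unadjusted | Power, adjusted |
|---|---|---|---|
| 5% | 0.044 | 0.814 | 0.821 |
| 10% | 0.039 | 0.820 | 0.841 |
| 20% | 0.028 | 0.834 | 0.881 |

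Simulation (12,000 runs per setting, N = 128) agrees: unadjusted power is 0.81–0.83 and adjusted 0.82–0.88. The amount forgone is about 1 to 5 points.

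**Step 4: simple randomisation within site** (same simulation).

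| f | Alpha, unadjusted | Power, unadjusted | Power, adjusted |
|---|---|---|---|
| 5% | 0.050–0.052 | 0.796–0.803 | 0.815–0.820 |
| 10% | 0.047–0.049 | 0.796–0.801 | 0.833–0.835 |
| 20% | 0.047–0.051 | 0.799–0.800 | 0.873–0.874 |

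Ranges are over the two site shares. Mean bias is about 0 throughout. The amount forgone is about 2 to 7 points.

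**Step 5: chance imbalance under simple lists.** The difference between arms in second-site share has SD √(p(1 − p) × 2/64), which is 8.8 percentage points at p = 50% and 7.7 at p = 25%. A gap of 10 points or more has probability about 26% or 19%. With a 1-point site difference, a 10-point gap moves the arm difference by 0.10 × 1 = 0.10 points, against a standard error of 0.354.

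**Step 6: one site.** None of steps 2 to 5 applies.

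**The case against.** The strongest reply is that the trial may have one site. The précis says so, Section 5.3 names one pharmacy service, and recruitment is projected from one hospital. The site-specific wording would then be an editing matter. This stands as a condition: the statistical part applies only if more than one pharmacy randomises. It does not remove the contradiction, because the multi-site wording runs through the design, pharmacy, visit and monitoring sections.

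A second reply is that Section 7.2 already provides for imbalance and that its open-ended list could admit site. That is correct, but only for a sensitivity analysis chosen after the baseline data are seen. The primary comparison stays unadjusted.

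The reply also defeats two stronger readings.

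- A reader might infer that randomising separately at each site makes the arms unbalanced by site and biases the comparison. It does not. Separate lists amount to stratification by site, and blocked lists would balance the arms. Chance imbalance is possible because no blocking is stated, and one unstratified central list would carry the same risk. The pooled test's standard error already allows for it. Systematic bias would need allocation ratios that differ between sites, which nothing in the documents suggests.
- A reader might infer that power falls below 80%. Figures of 78% down to 71% arise if SD 2.0 is read as the within-site SD and the variance from a 1- to 2-point site difference is added on top. Section 7.1 uses 2.0 as the SD of a pooled t-test, so it is most naturally the total SD. On that reading unadjusted power does not fall below the plan.

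**Conclusion.** The concern holds as a contradiction in the text and, conditionally, as an inefficient analysis. The documents do not settle the number of sites, who randomises, or the list structure; that conclusion needs no assumption. If the pharmacies randomise by site, the primary and secondary tests leave out a factor of the randomisation.

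Validity is not threatened under equal allocation. With blocked site lists the test is conservative. With simple lists it is correctly sized but less precise than it could be. The power forgone, about 1–5 and 2–7 points respectively, is measured against a site-adjusted analysis and is not a shortfall from the planned 80%. These sizes rest on the assumed site shares and 5–20% variance range. The documents cannot narrow them, and the upper end needs an extreme site difference. The change is worth making because it costs almost nothing.

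**What to change.** First, state the number of sites and who randomises, and make the précis, Abstract and Sections 2, 3.1, 5.3, 5.8, 5.9.1, 5.9.2, 6, 8.6.1 and 8.6.2 agree.

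If more than one pharmacy randomises:

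- specify a 1:1 permuted-block list per site, or one central list stratified by site;
- include site in the primary and secondary comparisons in Section 7.2, by a linear model with treatment and site or by a site-stratified Wilcoxon test.

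The cost is a list specification for the pharmacies and one or two degrees of freedom. No patients or visits are added, and 64 per arm can stand.

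If there is one site, remove the multi-center and site-specific randomisation wording. The analysis then needs no change on this account.
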